 10. 11. 12. 13. 14. 15. 16. 17. 18. 	Products, Devices, Techniques, and Tools.22Safety Reporting22Statistics and Analysis26Data Management28Quality Assurance Procedures30Ethical and Regulatory Considerations32Finance and Insurance33Publication and Registration Policy34References35

Bwrdd Iechyd Prifysgol Caerdydd a'r Fro Cardiff and Vale University Health Board

٦

1. Study Synopsis

Study Title	A pilot study investigating the effects of a manuka honey sinus rinse on sino-nasal outcome test scores in cystic fibrosis patients.				
Short Title	Manı	Manuka honey sinus rinse study – V0.1			
Study Design	Basic	Basic Science (feasibility / pilot study)			
Planned Sample Size	20-40) Participan	ts		
Planned Study Period	18 M	onths			
Planed Study Period		Start:	01/10/2018	Finish:	31/03/2020
Primary Objective	Does the addition of manuka honey to the sinus rinse impact on the Sino Nasal Outcome Test (SNOT)-22 score of patients with cystic fibrosis?				
Secondary Objective(s)	1. Does the addition of manuka honey to a sinus rinse alter the quality of life of patients with cystic fibrosis?				
	2.	Does the addition of manuka honey to a sinus rinse impacton the bacterial type/amount found in the nasal/paranasal cavities of patients with cystic fibrosis?			
	Does the addition of manuka honey to a sinus rinse protocolchange the structure of sputum mucus in patients with cystic fibrosis?				
Statistical Methodology & Analysis	Sino-nasal outcome tests and quality of life (questionnaire) scores will be compared before and after treatment with/without the manuka honey sinus rinse. Proportional change in bacteria seen within and between groups will be analysed using a contingency table and assessing co-variants. The molecular structural changes to sputum mucus will be corrected and vector normalized.				

Bwrdd Iechyd Prifysgol Caerdydd a'r Fro Cardiff and Vale University Health Board

2. Abbreviations

AE	A dverse E vents
AMR	A nti m icrobial R esistance
APR	Annual Progress R eport
AWACFC	A ll W ales A dult Cystic F ibrosis C entre
BMI	Body Mass Index
CF	C ystic F ibrosis
CFQ-R	C ystic F ibrosis Q uestionnaire - R evised
CI	C hief I nvestigator
CRF	C ase R eport F orm
СТ	C omputed T omography
ECFSPR	E uropean Cystic F ibrosis S ociety P atient R egistry

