A clear picture that has emerged from the application of microbiome analysis to CF lung infections is that as patients age, accumulating multiple rounds of potent antibiotic therapy, the diversity of the bacteria in the lung reduces. Their infections become dominated with AMR infections such as Pseudomonas and Burkholderia. This low diversity state is commonly associated with severe lung disease and inflammatory damage (Li 2016).

The proposed sample size combines a power calculation and a consideration of logistical constraints. We expect to see 290 patients per year of which 50% should complete a SNOT-22 form. Of the 145 forms received around 72 (50%) should be above average. If we allow for a low recruitment rate (of 30-40%) we believe it is realistic to enrol at least 20-30 patients per year. Over the 18 months of the project we feel, therefore, a sample size of 30-40 can be realistically achieved. Savastano (2014) published summary details of SNOT-22 scores for CF patients (who should well approximate our sample group) reporting a mean (SD) scores of 30.5 (14.5). We draw our definition of a clinically significant change from Hopkins et al (2009), who propose 8.9 points. The study will be structured as a 2-sided equality trial, with before and after measurements for each participant. In order to obtain a power of 80% we would require a sample size of at least 21.

We appreciate that the numbers of participants that will be recruited for this study, within the time frame (between 20-40 in 18 months), is not a true representation of the national population of CF patients. However, the results of this feasibility/pilot study will identify any trends in the effects of a nasal rinse supplemented with manuka honey on the bacterial amount/diversity within the infected sinuses. Antimicrobial interventions that do not rely on antibiotics to remove resistant strains from sinus infections have the potential to help alleviate symptoms in the sinus and upper airways, which may impact on the bacteria seen in the lower airways (Aanaes, 2013). Therefore, if a change in Project Proposal – V6.0 - 07/09/2020

bacterial diversity or a reduction in symptoms is observed, this study could inform a more in-depth study as manuka honey has already been demonstrated to eradicate both antibiotic sensitive and AMR bacteria in vitro and from chronic in vivo wounds.

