4.2 Secondary Objectives

Objective	Outcome Measure / Endpoint
Does the addition of manuka honey to a sinus rinse alter the quality of life of patients with cystic fibrosis?	Quality of life questionnaires (CFQ-R) will be completed before and after the use of a sinus rinse with/without manuka honey.
Does the addition of manuka honey to a sinus rinse impact on the bacterial type/amount found in the nasal/paranasal cavities of patients with cystic fibrosis?	Swabs, a sinus rinse wash sample and a sputum sample for each participant will be collected before and after the use of a sinus rinse with/without manuka honey. Bacteria amount and types will be analysed in each sample.
Does the addition of manuka honey to a sinus rinse protocol change the structure of sputum mucus in patients with cystic fibrosis?	Sputum samples from each participant will be analysed before and after the use of a sinus rinse with/without manuka honey by fourier transform infrared spectroscopy.

Bwrdd lechyd Prifysgol Caerdydd a'r Fro Cardiff and Vale University Health Board

5. Study Design

This is a single site study to be run at the AWACFC based in University Hospital Llandough (Cardiff and Vale Health Board) when patients attend any routine clinic meeting. The work on site will be carried out by the clinical research team as per the delegation of duties log.

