10.2 Techniques and Tools

SNOT-22 Questionnaire.

The SNOT-22 questionnaire is a validated method used to determine the severity of the social/emotional consequences of a patient's nasal disorder. This questionnaire has no right or wrong answers and should reflect the feelings of the patient to their nasal disorder (ranging from "no problem" through to a "moderate problem", with "problem as bad as it can be" having the highest rating). Some of the areas surveyed in this questionnaire relate to; sneezing, runny nose, dizziness, nasal discharge, ability to sleep, fatigue etc...

CFQ-R Questionnaire.

The CFQ-R questionnaire is used to understand the impact of CF and the associated treatments on the patients everyday life, allowing adjustments to be made in treatments to benefit the patient. The CFQ-R is a quality of life questionnaire that has been specifically designed for CF patients. Some of the areas surveyed in this questionnaire relate to; demographics, quality of life, school/work and daily life activities, and symptom difficulties.

CRF.

The CRF is used to record various data pertaining to the patient's demographics, antibiotic usage, comorbidities, and specific information relating to their condition (CF) and their treatment. This form is based on facts rather than the previous two questionnaires which focus more on the patient's feelings.

Microbial Diversity Assessment (Basic Microbiology).

Basic microbiological techniques (culturing bacterial species on selective bacterial growth media) will be used to determine the total number of bacteria in each biological sample. The selective growth media will provide some indication as to the bacterial species present in the samples and the ratio of them.

Microbial Diversity Assessment (Bioinformatics).

Advanced bioinformatics techniques (sequencing of bacterial cells) will be used to determine the community composition and the species of bacteria present within biological samples. This particular method will allow non-culturable bacterial cells to also be identified (which wouldn't be picked up through basic microbiology methods).

Sputum Mucus Structure.

Bruker Tensor high throughput Fourier transform infrared spectrometers will be used to determine the molecular structure of mucus sputum.

11. Safety Reporting

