12.1 Description of Statistical Methods

Qualitative analysis will include the difference between the SNOT-22 and quality of life questionnaire (CFQ-R) scores being assessed before and after treatment within and between both patient groups (with/without manuka honey). To determine if manuka honey caused a change in the amount/type(s) of bacteria present compared to the control group, a contingency table with odds ratio will be prepared taking into account co variants. Infrared spectra will be baseline corrected and vector normalised. Absorbance from specific infrared wavenumbers representative of mucin glycan molecular structures will be compared against in-house sputum spectral libraries to determine increase or decrease in glycosylation patterns as well as structural changes post-treatment. Comparisons in absorbance at key wavenumbers between groups will be analysed using ANOVA.

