12.2 Number of Participants

The proposed sample size combines a power calculation and a consideration of logistical constraints. We expect to see 290 patients per year of which 50% should complete a SNOT-22 form. Of the 145 forms received around 72 (50%) should be above average. If we allow for a low recruitment rate (of 30-40%) we believe it is realistic to enrol at least 20-30 patients per year. Over the 18 months of the project we feel, therefore, a sample size of 30-40 can be realistically achieved.

Savastano (2014) published summary details of SNOT-22 scores for CF patients (who should well approximate our sample group) reporting a mean (SD) scores of 30.5(14.5). We draw our definition of a clinically significant change from Hopkins et al (2009), who propose 8.9 points. The study will be structured as a 2-sided equality trial, with before and after measurements for each participant. In order to obtain a power of 80% we would require a sample size of at least 21. We therefore propose that a target sample size of 30, since this will be both achievable and will deliver sufficient power, even allowing for drop outs.

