12.3 Analysis of Outcome Measures/Endpoints

All participant data will be analysed by the academic research team after the end point of the study. The data will be sorted into the two treatment groups before analysis is carried out. The

primary outcome measures will be to determine whether the SNOT-22 score of the manuka honey treatment group has improved compared to the standard treatment. The secondary outcomes will be to see if; the lifestyle questionnaire scores have improved, the amount/type(s) of bacteria has changed, and whether the structure/composition of sputum mucus has changed in the same two groups. If any participants withdrew before the second visit/second set of samples were taken then that data will be excluded from analysis.

Bwrdd lechyd Prifysgol Caerdydd a'r Fro Cardiff and Vale University Health Board

13. Data Management

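### Bacterial amount is a culture count at both visits, but the only analysis named for it is a contingency table with odds ratio, which plans no estimate of the size of any change in load

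*Combined protocol and SAP*

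**What the plan says.** The second secondary objective in section 4.2 asks "Does the addition of manuka honey to a sinus rinse impact on the bacterial type/amount found in the nasal/paranasal cavities", and its endpoint reads "Bacteria amount and types will be analysed in each sample". Swab, rinse wash and sputum are collected at both visits (sections 4.2, 9.1 and 9.6). Section 10.2 says that basic culture methods "will be used to determine the total number of bacteria in each biological sample", so amount is recorded as a number, with a baseline for each participant.

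The analysis is given in two places. Section 12.1 states that "a contingency table with odds ratio will be prepared taking into account co variants". The synopsis states: "Proportional change in bacteria seen within and between groups will be analysed using a contingency table and assessing co-variants". Section 12.3 asks whether "the amount/type(s) of bacteria has changed" and adds no method.

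For bacterial load, the supplied text gives no cut-off, transformation, mean or ratio difference, or confidence interval. Section 12.1 does name a method for continuous data, ANOVA, but only for infrared absorbance.

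**The concern.** A contingency table needs categories and a culture count is not one. On the most natural reading, each count or its change between visits is sorted into classes such as 'declined' and 'did not decline', and the arms are compared on the odds. That answers how often load fell. It does not say by how much, and two participants with very different falls count the same. With no cut-off stated in advance, the split could also be chosen once the data are in hand.

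The other possible reading is that bacterial counts themselves fill the cells. That would give a kind of ratio, but bacteria from one sample would be treated as independent units and the pairing of visits within a participant would be ignored. Its standard error would have no sound basis.

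Section 3 says the pilot "will identify any trends in the effects of a nasal rinse supplemented with manuka honey on the bacterial amount/diversity within the infected sinuses" and could inform a more in-depth study. A later study would want the size and spread of the difference in load. The point concerns amount only; a table with an odds ratio suits bacterial type.

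**Working it through.** **The plan's own figure.** None is stated for bacteria. The 21 in section 12.2 is for SNOT-22: (14.5 × (1.960 + 0.842) / 8.9)² = 20.83, rounded up to 21. It reproduces but has no bearing here.

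**Inputs.** From the documents: "We therefore propose that a target sample size of 30" (section 12.2), a planned range of 20 to 40 (synopsis), and two-sided testing. Assumed: 1:1 allocation (15 per arm), a 5% level, normally distributed log10 counts with equal SD at both visits, before/after correlation r, no missing samples, and a 'declined' split (Visit 2 below Visit 1).

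**Step 1: what the odds ratio leaves open.** Take a 0.8 SD difference and no mean change in controls. The control probability of a decline is 0.5; in the honey arm it is Φ(0.8 / √(2 − 2r)).

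| r | P(declined), honey | Odds ratio |
|---|---|---|
| 0.3 | 0.751 | 3.0 |
| 0.5 | 0.788 | 3.7 |
| 0.7 | 0.849 | 5.6 |

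The SD of the log10 count does not enter, but the fold difference is 10^(0.8 × SD). For SDs of 0.5, 1.0 and 1.5 this is 2.5, 6.3 and 15.8. At r = 0.5 all three give the same odds ratio of 3.7.

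**Step 2: efficiency.** Simulated power (20,000 trials per setting), 15 per arm, 0.8 SD:

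| Analysis | r = 0.3 | r = 0.5 | r = 0.7 |
|---|---|---|---|
| ANCOVA on log count | 58% | 67% | 83% |
| t-test on change in log count | 44% | 56% | 78% |
| Odds ratio adjusted for Visit 1 count (likelihood ratio) | 39% | 47% | 61% |
| Chi-square, unadjusted | 30% | 38% | 56% |
| Fisher, unadjusted | 16% | 22% | 37% |

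With no true effect, the likelihood-ratio test rejects in 6–7% of trials, chi-square in just under 5% and Fisher in under 2%. The Fisher row therefore overstates the cost of categorising alone. Held at 5%, the adjusted odds ratio has 42% power at r = 0.5.

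Across effects of 0.6 to 1.0 SD and r of 0.3 to 0.7, ANCOVA gains 11–23 points over the nominal adjusted odds ratio and 19–35 over chi-square. Of the gain over chi-square, about 3–17 points come from ANCOVA's use of baseline, and the rest from not categorising.

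For totals of 20 and 40 (0.8 SD, r = 0.5): ANCOVA 47% and 80%, adjusted odds ratio 36% and 57%, chi-square 24% and 49%.

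**Step 3: cultures below detection.** Setting them to the detection limit and running ANCOVA shrinks a true 0.8 SD difference to about 0.53 SD if 20% of Visit 1 cultures are below the limit, and to about 0.35 SD if 40% are. A censored-normal model gave medians of about 0.77 and 0.81 SD. The fix therefore should not rest on simple substitution.

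**The case against.** The strongest reply is that the fault is inferred. Nowhere do the documents say that counts will be split. Section 12.1 covers amount and type in one sentence and leaves its covariates open. A reader might infer that the plan commits itself to dichotomising at 'declined'; the text does not support that. It shows a method that cannot be applied to a count without a further step that is not described.

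The covariates could include the Visit 1 count. That would recover some power, as Step 2 shows, but would still yield no size of effect. The synopsis phrase about proportional change could mean a shift in the mix of species, since section 10.2 says selective media will indicate species ratios. That may be so, but section 12.1 still sends total amount to the table.

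A reader might also infer that the pilot could tell a later study nothing about load. That goes too far. Counts exist for each participant at both visits, and their mean change and SD could be computed whatever test is named. Section 12.3 asks only whether amount has changed, which an odds ratio can address.

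Nor is this a failure of claimed power: the plan claims none for bacteria. The figures depend on the scenario. Controls begin a standard rinse, and current rinse users are excluded, so some control decline is plausible. With a 0.5 SD fall in controls (0.8 SD difference, r = 0.5), the probabilities are Φ(1.3) = 0.903 and Φ(0.5) = 0.691, the odds ratio is (0.903/0.097) / (0.691/0.309) ≈ 4.2, and chi-square power is about 31%.

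Finally, section 9 points to an attached study procedures document that was not available to check. It might add detail, though section 12.1 would still need to agree with it.

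**Conclusion.** The point holds as a cheap improvement to a secondary analysis. The supplied text names only a contingency table with odds ratio for a quantity measured as a count at both visits, and neither plausible use of that table gives a valid estimate of how much load changed. This conclusion rests on the wording and on Step 1, not on power.

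Under the stated assumptions (15 per arm, 0.8 SD, r = 0.5, 'declined' split), the efficiency cost is about 20 points of power if the odds ratio is adjusted for the Visit 1 count (67% against 47%) and about 28 points by unadjusted chi-square (67% against 38%, before rounding). These figures illustrate and do not predict.

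The proposed estimate would itself be imprecise. The ANCOVA 95% interval has a half-width of about 0.65 SD at r = 0.5, which for a log10 SD of 1.0 is a factor of 10^0.65 ≈ 4.5 either way. The gain is a planned estimate with its uncertainty shown. The SNOT-22 primary outcome is unaffected.

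**What to change.** In section 12.1, with the synopsis made to match:

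> For each sample type (swab, rinse, sputum), log10 total bacterial count at Visit 2 (per mL or per swab, with the plates that make up the total stated in advance) will be compared between arms, adjusting for the Visit 1 log10 count, and reported as a ratio of geometric means with 95% CI. If any cultures are below the detection limit, their number will be reported by arm and visit, Visit 2 values will be treated as left-censored (censored-normal regression), and a rank-based ANCOVA will be given as sensitivity analysis. Bacterial types (presence or absence) will be analysed by contingency table with odds ratio, as planned. These are exploratory secondary estimates without multiplicity control.

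The wording should also say how a Visit 1 value below the limit enters as a covariate; setting it at the limit is one workable choice.

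**Cost.** No new samples, visits or participants are needed, only a little more analysis work. The laboratory must state its detection limit, which the documents do not give. The censored model assumes normality and loses precision when many cultures are below detection. Three sample types mean several tests: if independent at 5%, the chance of at least one false positive is 1 − 0.95³ = 14%. The results should therefore be read as estimates with intervals.

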Between 20-40 patients will be recruited for this study over an 18-month period. Patients will be recruited opportunistically during their routine clinic meetings. Normally the AWACFC runs a clinic for CF patients everyday Monday to Friday. We would estimate recruiting an average of two patients per month, taking into account the inclusion/exclusion criteria (see below), and the potential for participants to drop out of the study. We would expect to recruit all patients within the 18-month period.

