9.4 Randomisation, Blinding, and Unblinding

A blocked randomisation list will be generated prior to start of study using the electronic random number generator tool (see below). The participants of the study will not be blinded to the treatment they are receiving because the addition of manuka honey to the sinus rinse is obvious and there is no way to negate this. The academic research team will be blinded to which groups the participants (only identifiable by their participant ID number) are assigned. This information (the group allocations and treatment regimens) will only be made available to the academic research team once analysis of the data begins.

- GraphPad QuickCalcs
 - o https://www.graphpad.com/quickcalcs/randomize1/

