9.5 Baseline Assessments

General information will be collected from participants via the clinical record as will information pertaining to their antibiotic usage, their comorbidities, and more specific cystic fibrosis information as per below:

- Age.
- Sex.
- Height
- Weight.
- BMI.
- Smoking status.
- Antibiotic usage (last three months).
 - IV antibiotics.
 - Oral antibiotics.
 - Nebulised antibiotics.
 - Long term antibiotic usage.
- Co-morbidities.
- Cystic Fibrosis specific information.
 - o SNOT-22 score
 - \circ $\;$ FEV1% score. .
- Is the participant undergoing sinus treatment.
- Is the participant used a nasal spray.
- Is the participant recovering from endoscopic surgery.

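### The covariate-adjusted odds ratio for bacteria has no covariate limit and no sparse-data method at about 15 per arm, so for less common organisms it will often be unusable

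*Combined protocol and SAP*

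**What the plan says.** For the effect of honey on bacteria, section 12.1 states that "a contingency table with odds ratio will be prepared taking into account co variants". The synopsis has a similar sentence: "Proportional change in bacteria seen within and between groups will be analysed using a contingency table and assessing co-variants". Neither place names a covariate, an estimator, the event that is counted, or what is done when a cell is empty.

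On numbers, section 12.2 says "We therefore propose that a target sample size of 30", and section 8 gives a wider range: "Between 20-40 patients will be recruited for this study over an 18-month period". Section 9.4 specifies a blocked list for two groups without an allocation ratio. Section 12.3 reduces the analysed number further: "If any participants withdrew before the second visit/second set of samples were taken then that data will be excluded from analysis".

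Section 9.5 lists about 16 baseline items, including age, sex, body size, smoking, four kinds of antibiotic use, comorbidities, SNOT-22, FEV1% and sinus treatments. It does not call any of them a covariate, and no other section selects or excludes one.

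**The concern.** An odds ratio needs carriers and non-carriers in both arms. With 15 per arm and an uncommon organism, one arm can easily have no carriers. The odds ratio is then zero, infinite or undefined, and the usual interval is not available. Each added covariate divides a handful of positives further. Section 10.2 plans sequencing to identify the species present, so uncommon organisms will be among the results.

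The rationale in section 3 says that the pilot should pick up trends and inform a more in-depth study. An estimate that does not exist, or that shifts with the number of covariates chosen, does that poorly. An open choice of covariates also lets the model be settled after the results are seen.

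**Working it through.** **The plan's own calculation.** The only sample-size figure is for SNOT-22 (section 12.2). With SD 14.5, difference 8.9, 80% power and two-sided alpha 0.05 (alpha assumed), the before/after formula gives ((1.960 + 0.842) × 14.5/8.9)² = 20.8, so 21. This reproduces the stated figure, but as a one-group calculation on a score. It gives no support for the bacterial odds ratio.

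**Inputs for the check.** 15 per arm (target 30, 1:1 assumed). Control carriage 50%, 33%, 20% and 10%, all assumed. The 33% echoes the *P. aeruginosa* share in section 3, which refers to lung infections and not to the sinuses. True odds ratio 0.40, assumed.

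**Step 1: empty cells in the plain 2×2 table (exact).** Honey-arm carriage is p1 = 0.40·o/(1 + 0.40·o), where o = p0/(1 − p0). An arm has an empty cell with probability z(p) = (1 − p)^15 + p^15. The chance of at least one empty cell is 1 − (1 − z(p0))(1 − z(p1)). Expected positives are 15(p0 + p1).

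| Control carriage | Honey carriage | Expected positives | z(p0) | z(p1) | Any empty cell |
|---|---|---|---|---|---|
| 50% | 28.6% | 11.8 | <0.001 | 0.006 | 1% |
| 33% | 16.5% | 7.4 | 0.002 | 0.067 | 7% |
| 20% | 9.1% | 4.4 | 0.035 | 0.239 | 27% |
| 10% | 4.3% | 2.1 | 0.206 | 0.521 | 62% |

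With no effect at all and 10% carriage, the chance is 1 − (1 − 0.9^15)² = 37%. That divides into about 16% zero, 16% infinite and 4% undefined.

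**Step 2: one covariate, ordinary maximum-likelihood logistic regression (simulated).** There was no usable fit in about 1%, 9%, 38% and 72% of trials at 50%, 33%, 20% and 10% carriage. A repeat with one unrelated binary covariate (1,500 trials per setting) separated two kinds of failure:
- Either coefficient had no finite value in 2%, 10%, 37% and 74%.
- The arm coefficient itself was lost in 1%, 7%, 28% and 63%, close to the exact figures above.

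The larger figures therefore describe a fit that fails. The smaller ones describe an arm odds ratio that is itself zero, infinite or undefined.

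**Step 3: a stratified table does not avoid this.** With a true odds ratio of 1/3 and one strongly prognostic binary stratifier, the Mantel-Haenszel odds ratio was zero or undefined in 4%, 9%, 23% and 56% at the same four carriage levels.

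**Step 4: bias.** At 33–50% carriage the median finite estimate is close to the true 0.40 with one covariate, and about 0.24 to 0.36 with three to eight. At 10% carriage it moves the other way: with a true odds ratio of 1/3, finite estimates averaged 0.48 to 0.54 with one to three covariates.

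**Step 5: recruitment range.** Plain table, true odds ratio 1/3, for totals of 20, 30 and 40: any empty cell in 23%, 10% and 5% at 33% carriage, and in 51%, 33% and 21% at 20% carriage.

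**Step 6: precision.** With a true odds ratio of 1/3, one covariate and 33–50% carriage, the upper 95% limit is typically 34 to 48 times the lower one.

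**Step 7: the alternative.** Firth regression with arm and one covariate always gave a finite estimate. Its median was about 0.40 to 0.44 against a true 0.40 at 20–50% carriage, and about 0.5 at 10%.

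**The case against.** A reader might infer that the plan commits to ordinary logistic regression on all the section 9.5 items, that it would therefore fail in most trials, and that it exaggerates honey's effect whenever it can be computed. The documents do not support that.

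- Section 12.1 names no model. A stratified or exact analysis fits its wording equally well.
- Section 9.5 is a data-collection list. Several items overlap (height, weight and BMI), and one is largely removed by the exclusion of recent sinus surgery. High failure rates with many covariates are therefore hypothetical.
- For an organism carried by a third to a half of controls, failure with one covariate is between about 1% and 10%, and the bias is small.
- Inflation and non-existence mostly occur in different settings. Inflation needs a commoner organism and about three or more covariates. Where non-existence is frequent, the finite estimates are attenuated.
- An odds ratio of zero is not the same as no result, because it can be reported with an exact upper bound.
- This is one secondary objective in a pilot, and no decision threshold depends on it.

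All of this stands, and it limits the claim. It does not remove the gap: the section that should say how sparse tables are handled and which covariates enter says neither.

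**Conclusion.** The point holds as one of under-specification with a measurable consequence. At about 15 per arm, an ordinary odds ratio adjusted for one covariate is rarely a problem at 50% carriage (roughly 1% of trials without a usable fit) and an occasional one at 33% (9%). It is frequently unusable at 20% (38%) and usually unusable at 10% (72%). Counting only trials in which the arm odds ratio itself is lost gives about 1%, 7%, 28% and 63%.

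These figures rest on 1:1 allocation, 30 participants analysed, a true odds ratio of 0.40, and carriage levels that the documents do not supply. Withdrawals or recruitment near 20 would raise them; 40 participants would lower them. A general claim that the planned analysis overstates honey's effect is not supported: the direction of bias depends on carriage and on the number of covariates. Even where the odds ratio exists, its interval will be very wide, so no method turns this into a confirmatory result. The change is worth making because it is cheap and the better method uses data already being collected.

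**What to change.** Amend section 12.1 and the synopsis as follows, for each specimen type and organism:

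1. State what counts as positive.
2. Estimate the between-arm odds ratio at Visit 2 by Firth-penalised or exact logistic regression, with arm and the same organism's Visit 1 status as the only covariate. Samples from both visits are already in sections 9.1 and 9.6.
3. Alongside it, report the honey-minus-standard difference in the proportion positive with a Newcombe 95% interval, which exists even when a cell is empty.
4. Keep the within-group before/after description, and analyse bacterial amount separately as a quantity.
5. Describe the other section 9.5 items by arm and keep them out of the model.
6. Label the bacterial results exploratory.

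The cost is wording only, with no new data or visits. The downside is that chance imbalance in the other baseline items is described rather than adjusted for. The estimates remain imprecise, and for rare organisms the penalised estimate is still pulled towards 1.
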